# **Abbreviations and Definitions**

ACL	Anterior cruciate ligament	JHFT	Jump Height by Flight Time
AE	Adverse Event	MRI	Magnetic resonance imaging
AREF	Andrews Research and Education	OKC	Open Kinetic Chain
Found	ation	PI	Principal Investigator
CRF	Case Report Form	PRO	Patient Reported Outcomes
DHHS Service	S Department of Health and Human	RTP	Return to Play
EDC	Electronic Data Capture	RTS	Return to Sport
FMS	Functional Movement Screening	QA	Quality Assurance
GCP	Good Clinical Practice	SAE	Severe Adverse Event
HIPA	A Health Insurance Portability and	SOC	Standard of Care
	entability Act	SOP	Standard Operating Procedure
$H_0$	Null Hypothesis	TSK	Tampa Scale for Kinesiophobia
$H_1$	Alternative Hypothesis	YBT	Y Balance Test
IRB	Institutional Review Board		

Version: 1.0

**Background / Scientific Rationale** 

It is estimated that 250,000 anterior cruciate ligament (ACL) injuries occur in the United States

per year (Griffin et al., 2000, Gianotti et al., 2009). With ACL injuries being one of the most

frequent injuries in both contact and noncontact sports, medical professionals need reliable tools

to treat injured athletes and return them to sport in a safe/timely fashion (Harris et al., 2013).

Along with the prevalence of initial injury, reinjury rates may be up to 30% in young active

patients who undergo ACL surgical interventions. With the rate of return to competitive play

post-ACL injury being 55%, it is imperative to create a systematic quantitative algorithm to

safely return athletes to competitive play after ACL injury (Ardner et al., 2014). In addition to the

primary injury often there is additional concern for instability of the knee, increased joint laxity,

reduced activity and participation, as well as an increased risk of knee osteoarthritis in the future

for the athlete (Lohmandeder et al., 2004). Along with the play time missed for the athletes, ACL

injuries are associated with significant physical and mental harm as well as a lower health-related

quality of life which supports the need for effective Return to Sport assessments. However, the

current literature is limited regarding the standardization and data-driven decision in regards to

return-to-sport algorithms (Creighton et al., 2010). Return-to-sport algorithms require further

development.

Regenerative medicine technologies have the potential to expedite return to sport times after

injury and surgery. However, to objectively study the application of regenerative medicine

technologies to ACL injury and surgery, the development of an objective measurement system

for the safe and appropriate return of patients to sport is required. Ensuring patients are being

safely returned to their sports after treatments for ACL injuries is important to decrease the risk

of reinjury. As noted in Grindem et al. (2016), athletes returning to sport with asymmetrical

Version: 1.0

Version Date: 10NOV2021

quadricep strength have a significant risk increase for reinjury. After sustaining injury and operative intervention, a systematic evaluation process is needed to evaluate athletes' progress towards returning to sport. To safely return to sport, an athlete must restore range of motion, strength, and stability and control across the affected and unaffected knee (Wilk et al., 2012; Bodor, 2001). With current advancements in technology, an up-to-date quantitative return to sport algorithm is presented. Multiple measures are required to capture the risk factors for reinjury such as imbalances and weaknesses that are not always evident in observation. The purpose of this study is to develop the Andrews ACL S.C.O.R.E (Subjective Clinical Outcome Return to Play Evaluation.) Development will begin with baseline measures and re-evaluation during the rehabilitation progression to address asymmetries and movement inefficiencies in a data driven manner with the ultimate goal of returning to play safely, without reinjury. A modern return to sport algorithm will include patient reported outcome measures, objective/modern strength and ability testing, and MRI evaluation of the reconstructed ACL tissue. Ardern et al. (2014) report the importance of assessing the psychological factors that impede athletes from returning to sport after ACL reconstruction. To address these individualized factors, patient reported outcomes are used to quantify these measures.

A comprehensive assessment is required to ensure an athlete's ability to safely return to sport is identified. This Return to Sport assessment must incorporate the overall health of the individual and assess specific measures of the affected ACL area. These qualities of assessment include the need for their strength to be at or near their preinjury level with symmetry to the non-injured leg, range of motion at or near their preinjury level with symmetry to the non-injured leg, joint stability at or near their preinjury level with symmetry to the non-injured level and confidence in movement comparable to the confidence in movement to the non-injured leg. As found by

Version: 1.0

Ardern et al. (2014) symmetry hopping in movement has positive predictive factors for returning

to competitive sport levels after ACL reconstruction. The functional movement screening

assessment, a low-cost assessment, is also widely used to assess current functioning level. This

assessment includes seven movement patterns to ensure the whole-body biomechanics can be

assessed. The FMS assessment will provide a quantitative assessment of functional movement

**Objective:** 

This project will develop a data driven decision making model to assess a competitive athlete's

readiness to return to sport after ACL injury and surgery safely. A specific audience and return to

activity level specification is required for complete return to sport studies (Gokeler et al., 2017).

This Return to Sport algorithm is targeting competitive pre-collegiate and collegiate athletes with

a return to sport that is congruent with their pre-injury level of play.

Return to Sport-Obtaining medical clearance to participate in competitive sports at the athlete's

pre-injury level

Safely- Returning to pre-injury competitive level without instances of reinjury of the same ACL

**Protocol Design** 

This will be a prospective cohort study of 100 competitive level pre-collegiate and collegiate

level athletes who have sustained an ACL injury requiring reconstruction with a length of

enrollment of 36 months.

**Hypotheses** 

Version: 1.0

Version Date: 10NOV2021

**Alternative Hypothesis:** 

The prospective capture of multimodal data will improve the safe return of athletes to sport after

ACL surgery and allow for the evaluation of regenerative medicine technologies to improve this

process.

Patient reported outcomes and return to sport times will correlate directly with MRI objective

scores and biometric strength/movement scores.

**Null Hypothesis:** 

The prospective capture of multimodal data will not show improvement in the rate of safe return

of athletes to sport after ACL surgery.

Patient reported outcomes and return to sport times will not directly correlate with MRI

objective scores and biometric strength/movement scores.

**Treatment Plan** 

For the one hundred participants recruited for this study, the duration of the treatment plan will

be 24 months. Each of the participants will be qualified for the study due to falling within all

inclusion criterion and no exclusion criterion. The screening of the inclusion criterion will occur

at visit one of the study. At this time, the AREF Research Team will review and collect informed

consent from each participant. Visit two will occur three (3) months after each participant's ACL

reconstruction surgery. At this time, an evaluation by the treating physician will occur along

with functional movement assessment and MRI. Visit three will occur six (6) months after each

participant's ACL reconstruction surgery. At this time, an evaluation by the treating physician

Version: 1.0

Version Date: 10NOV2021

will occur along with functional movement assessment and MRI. Visit four will occur nine (9)

months after each participant's ACL reconstruction surgery. At this time, an evaluation by the

treating physician will occur along with functional movement assessment and MRI. Visit five

will occur twelve (12) months after each participant's ACL reconstruction surgery. At this time,

an evaluation by the treating physician will occur along with functional movement assessment

and MRI. Visit six will occur eighteen (18) months after each participant's ACL reconstruction

surgery. At this time, an evaluation by the treating physician will occur along with functional

movement assessment and MRI. Visit seven will occur twenty-four (24) months after each

participant's ACL reconstruction surgery. At this time, an evaluation by the treating physician

will occur along with functional movement assessment and MRI. At each time point, the treating

physician or the therapist performing the functional movement assessment can choose to limit

the functional movement assessment if there are concerns that the patient may not be ready for

the expected load of one or more elements of the functional movement assessment.

At each monthly time point after ACL reconstruction patient reported outcomes will be collected

by the research team to assist in assessing the overall health and confidence in Return to Sport

for each athlete. The following patient reported outcomes will be collected in written or

electronic format after informed consent has been obtained from each participant: Sports

Participation, Reinjury, Tampa Kinesiophobia Scale, IKDC, PROMIS, SANE.

**Participation:** 

A total of 100 competitive pre-collegiate or collegiate athletes will be recruited for participation

in the Andrews Return to Sport algorithm study. Participants in the study will be individuals who

have provided informed consent to the research team to adhere to the provided research protocol.

Version: 1.0

Version Date: 10NOV2021

**Inclusion Criterion:** 

One hundred (100) pre-collegiate or collegiate level athletes will be included in this study. They

will fall within the following inclusion criterion:

1. Age 14-24 years

2. Require ACL reconstruction surgery

3. No other ligament injury which would require repair or reconstruction to lower extremity

is present as assessed by treating physician

4. Exhibits desire to return to pre-injury competitive level

5. Assessed to be in good physical health condition by the treating physician

**Exclusion Criterion:** 

1. Requires more than one ACL reconstruction surgery at time of screening

2. Has comorbid lower extremity diagnoses which would impede return to sport as assessed

by the treating physician

3. Does not desire to return to pre-injury competitive sport level

**Benefits:** 

Each study participant will be provided with a total five hundred dollars (\$500.00) for their

participation in the study through the 24-month period. The \$500.00 will be dispersed on the

following predetermined schedule. \$100.00 at Visit 2, \$100.00 at Visit 3, \$100.00 at Visit 5,

\$100.00 at Visit 6, and \$100.00 at Visit 7. If a participant withdraws from the study the

Version: 1.0

Version Date: 10NOV2021

monetary benefits will not be dispersed after the withdrawal date. However, there will be no

effect on the medical care provided if a participant withdraws from the study.

**Return To Sport Assessments:** 

**Isokinetic Strength Testing:** 

Isokinetic strength testing is crucial to assess the muscular strength of the quadricep and

hamstring after ACL reconstruction. Due to the high rate of reinjury with known predictive

factors due to imbalance in strength, a quantitative measure of balance of strength is required to

guide return to sport decision making. An isokinetic dynamometer will be used to assess knee

extensor and flexor strength (Riesterer et al., 2020). Isokinetic strength testing will support the

Andrews Return to Sport algorithm through multimodal functional assessments.

**Magnetic Resonance Imaging** 

Magnetic Resonance Imaging (MRI) will be used as a noninvasive assessment tool to obtain

quantitative measures to assess progress in graft maturity and rehabilitation towards safe return

to sport. As the injured ACL undergoes ligamentization, MRI will be used to monitor the

progress of each participant through T2\* analysis and volume at the following time intervals:

3months, 6months, 9months, 12months, 18months, and 24months. MRIs will review the

integrity of each graft, placement within the tunnel, and tunnel healing, and healing of the donor

site (Grassi et al., 2016).

Version: 1.0

Version Date: 10NOV2021

**Functional Movement Assessments:** 

The functional movement screening assessment (FMS) is widely used to assess current

functioning level and does not require significant monetary resources to provide this assessment.

This assessment includes seven movement patterns to ensure the whole-body biomechanics can

be assessed. The movements required are deep squat, hurdle step, inline lunge, shoulder

mobility, active straight leg raise, trunk stability push up, and rotary stability assessment. FMS

screening will be used to identify the precursor deficits which could lead to reinjury. These

deficits include increased anterior tibial shear force, decrease knee flexion, decreased hip flexion,

increased knee internal rotation, increased trunk flexion, and increased lumbar hyperextension.

The FMS assessment will provide a quantitative assessment of functional movement on a 0-3

scale as follows (Hoogenboom, Voight, Cook, & Rose, 2013).

3- Individual can perform the movement without any compensation.

2- Individual can perform the movement but must utilize poor mechanics and compensatory

patterns to accomplish the movement.

1- One is given if the individual cannot perform the movement pattern even with compensation.

0- Individual reports pain during activity.

**Single Leg Squats:** 

The single leg squat assessment is commonly used to evaluate the eccentric and concentric

contractions of the muscles in the upper leg, lower leg, and hip (Bailey et al., 2010). This test

was first executed and defined the method for performing by Livengood (2004) to assess

balance, strength, and the kinetic chain. To rate the single leg squat test, Livengood also assigned

Version: 1.0

Version Date: 10NOV2021

a scale to the test (Figure 1). Each participant will be instructed to squat down to approximately

60 degrees with a time constraint of six seconds while holding one leg suspended in the air.

When analyzing the movements within the single leg squat, researchers assess the functioning

and symmetry of following muscles and the activity associated: vastus medialis obliquus, gluteus

medius, hip flexion, hip abduction, and knee flexion (Table 1).

Jump Analysis:

The jump analysis highlights the importance of the monthly psychological data review

completed by the Kinesiophobia Scale. In review of this data, the psychological apprehension

will guide the functional jump analysis. The jump analysis will occur initially from both legs to

address psychological apprehension (Davies et al., 2017). From this assessment, calculation is

made based on the allometric scaling to each participant's height (Davies et al., 2017).

Additionally, flight time will be measured as defined by the time (s) when the participant's feet

leave the platform and subsequently contact the platform again (Jordan et al., 2020).

Additionally, the jump height by flight time (JHFT) will be measured. JHFT is defined as the

distance the marker on the malleolus moved from lowest point when in contact with the platform

to the highest point during the jump.

A single leg hop assessment will also be performed across both the injured and non-injured legs.

The score for this assessment is the distance travelled from the start to the location of the

posterior heel of the landing leg (Manske & Reiman, 2013). The variability of scores across the

injured and non-injured leg will be used as a measure of symmetry in function movement for

each athlete.

Version: 1.0

Version Date: 10NOV2021

Additionally, a double leg hop will be scored during the jump analysis. The score for this

assessment is the distance travelled from the start to the location of the posterior heel of the

landing leg (Manske & Reiman, 2013). Additionally the participant's jump will be assessment

for symmetry in takeoff and landing across both the injured and uninjured leg.

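### JHFT is named as a flight-time jump height but defined as ankle-marker travel, which is a different quantity

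*Protocol*

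**What the plan says.** The abbreviation list in the protocol expands JHFT as "Jump Height by Flight Time".

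The Jump Analysis section first sets up flight time as a variable of its own, in a sentence that opens "Additionally, flight time will be measured as defined by the time (s) when the participant's feet"; the interval runs from take-off until the next contact. The height is introduced next: "Additionally, the jump height by flight time (JHFT) will be measured. JHFT is defined as the". What follows that opening is a marker displacement. Its starting position is given by the words "distance the marker on the malleolus moved from lowest point when in contact with the platform", and its end by a separate phrase, "to the highest point during the jump".

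The protocol gives no formula that turns flight time into a height, and does not mention JHFT outside these two places. The strength and functional testing list in the appendix (3, 6, 9, 12, 18 and 24 months) has the single leg hop as its only jump test; neither JHFT nor flight time is on it.

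**The concern.** A height obtained from flight time and a height read from a marker are two measurement methods with different sources of error. The label promises the first and the definition prescribes the second.

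The stated start point makes this more than a naming slip. Counting from the marker's lowest position in contact means that the ankle's rise as the heel lifts is included before the athlete has left the platform. Bending the knees in the air raises the marker further without raising the body.

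What is at stake is interpretation. The alternative hypothesis expects patient reported outcomes and return-to-sport times to correlate with MRI scores and with strength and movement scores, and JHFT is one of the movement measures described. A constant offset would leave a correlation unchanged, but one that varies with technique would not. The same section links the jump test to psychological apprehension, so technique could plausibly vary with one of the variables under study. A reader of the results who takes the label at face value would also set these values beside flight-time heights from elsewhere, which would not be a like-for-like comparison.

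**Working it through.** The protocol gives no value for JHFT, so there is no figure to reproduce. The check compares the two definitions algebraically and then illustrates the gap.

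**Inputs from the protocol.** Flight time t runs from the feet leaving the platform to their next contact. JHFT is marker travel from the lowest point in contact to the highest point in the jump, taken here as vertical.

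**Inputs assumed, because the protocol gives none.** Flight times of 0.40 and 0.50 s; heel rise plus tuck of 5 to 15 cm; true jump height of 30 cm and landing drops of 10 and 20 cm for the second comparison; g = 9.81 m/s².

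**Formulas.** Let h be the rise of the body after take-off.

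- Height from flight time, with the same posture at take-off and landing: g × t² / 8.
- Marker travel as the protocol defines it: h + a + k, where a is the rise of the malleolus from its lowest contact position to its take-off position (heel rise) and k is any leg tuck at the top of the jump.

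With matching postures the first equals h, so the two agree only if a + k = 0.

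**Gap with matching take-off and landing posture.**

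| Flight time | g × t² / 8 | a + k = 5 cm | a + k = 15 cm |
|---|---|---|---|
| 0.50 s | 9.81 × 0.25 / 8 = 30.7 cm | 35.7 cm (5/30.7 = +16%) | 45.7 cm (15/30.7 = +49%) |
| 0.40 s | 9.81 × 0.16 / 8 = 19.6 cm | 24.6 cm (5/19.6 = +26%) | 34.6 cm (15/19.6 = +77%) |

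The percentages use heights rounded to 0.1 cm; with the unrounded 19.62 cm the second row becomes 25% and 76%. The same added distance weighs more on a lower jump.

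**Gap when the athlete lands lower than at take-off.** If the body is lower by d on landing, flight lasts longer: t = √(2h/g) + √(2(h + d)/g). Take h = 30 cm, a = 5 cm and k = 0, so that marker travel is 30 + 5 = 35.0 cm throughout.

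- d = 10 cm: t = 0.247 + 0.286 = 0.533 s, and g × t² / 8 = 34.8 cm. The two values are almost equal.
- d = 20 cm: t = 0.247 + 0.319 = 0.567 s, and g × t² / 8 = 39.4 cm. The flight-time height is now 4.4 cm larger.

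The sign of the gap therefore depends on technique, and no constant correction converts one quantity into the other.

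**The case against.** The best defence is that the protocol gives one explicit operational definition directly after the name. It supplies no flight-time formula that staff could use instead, and it never says that flight time and JHFT are to be combined or interchanged. On that view only the label is wrong. This has force: that different assessors would record different quantities is a possibility, not something the text shows. It does not remove the mismatch, because the abbreviation list repeats the label and the results would carry it.

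It can also be said that flight-time height is no cleaner, since a bent landing lengthens flight. That stands. It is why neither method is preferred here, and why a posture requirement belongs with the formula.

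Three stronger readings are tempting, and the protocol does not support them.

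- A reader might infer that the recorded heights are inflated in general. That holds for matching take-off and landing postures with some heel rise or tuck, but a strongly bent landing reverses it, as in the 39.4 against 35.0 cm case.
- A reader might take 16% to 49% as the expected error. It is an illustration at one assumed flight time; the protocol gives no flight time, heel rise or tuck.
- A reader might infer that comparisons between the injured and uninjured leg are distorted. The jump is introduced as starting from both legs, and JHFT is never said to be recorded per leg. The score compared between legs is the single leg hop, which is a distance travelled.

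**Conclusion.** The point holds as an inconsistency between name and definition. The protocol calls the measure a jump height by flight time and defines it by marker displacement, and these differ unless heel rise, tuck and any change of posture on landing are absent or happen to cancel. That conclusion rests on the text and on geometry, and needs no assumed number. The size of the gap cannot be derived from the protocol; the worked figures show only that it could be material and could take either sign.

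The consequence is minor. No endpoint, threshold or clearance rule names JHFT, and the appendix list omits it. It still merits correction, because the protocol commits to measuring it and it falls among the movement measures that the hypothesis proposes to correlate. A gap that differs between athletes or visits could affect that correlation; the protocol gives no basis for estimating by how much.

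**What to change.** Make the name and the definition agree, in one of two ways:

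1. Define JHFT = g × (flight time)² / 8, using the flight time that the Jump Analysis section already measures, and require the same body posture at take-off and landing.
2. Keep the marker method, rename it malleolus-marker displacement in both the Jump Analysis section and the abbreviation list, and state that it is not reported as, or pooled with, a flight-time jump height.

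Either resolves the inconsistency; the second leaves the measurement procedure unchanged. In both cases, state that one method is used at all visits. If recording has already begun, document which method produced the existing values before any are pooled.

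The cost is a sentence or two and no new measurement. The first option relies on flight time being recorded as the Jump Analysis section says; since the appendix testing list omits it, the list should be brought into line at the same time.
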